Attempts to image the aortic wall in order to predict AAA growth or rupture have been inconclusive. Existing imaging modalities include CT, MRI, and intravascular ultrasound, but these are limited by low accuracy, radiation exposure, availability, and safety issues. Recently, contrast ultrasound (CEUS) using microbubbles has emerged as a method for imaging adventitial vasa vasorum (VV) in carotid plaques. We have an active CEUS program and have previously correlated VV density with neovascularization in an animal model, and have imaged 850 patients with carotid CEUS. CEUS can also be used to image AAA, since neovascularization and VV are commonly seen on AAA wall histology. Both may be markers of hypoxia and weakening of the aortic wall, and can be quantified with CEUS using time–signal intensity curve analysis to detect VV density in different regions of interest in the AAA wall.

Our goal is to non-invasively study the metabolic processes within the aortic wall that are thought to explain AAA growth and rupture, and their variation with age and gender. This process also affects unstable coronary and carotid disease, where the progression from an asymptomatic plaque to rupture and thrombosis, also known as “vulnerable plaque”, is not

fully explained by the luminal diameter. Similarly, localized hypoxia, neovascularization, and inflammation of the aortic wall are thought to contribute to degeneration of AAA, accounting for growth and possibly rupture that are otherwise not explained by absolute AAA diameter. In addition, pro-inflammatory systemic biomarkers, such as interleukin, tumor necrosis factor- α ; and matrix-degrading enzymes, are up regulated in patients with AAA suggesting a systemic inflammatory process. Non-invasively detecting AAA wall neovascularization using CEUS is a novel approach to evaluate aortic wall vulnerability. It could identify regional inflammation, and propensity for AAA wall weakening, enlargement or rupture. Our hypothesis is that increased neovascularization of the aortic wall correlates with AAA growth and rupture and is more pronounced in women. CEUS imaging of AAA, coupled with serum biomarker measurements, has the potential to identify the propensity for growth or rupture. The Specific Aims are:

Aim#1: Determine the relationship between AAA growth rate and VV density. Approach: prospective CEUS imaging of a cohort of patients with AAA 4-5.4cm in diameter at 6 month intervals for 18 months. Hypothesis: VV density on CEUS is increased in AAA at risk for growth.

Aim#2: To correlate CEUS findings with serum biomarkers. Approach: longitudinally measure AAA specific serum biomarkers with every CEUS. Hypothesis: Levels of pro-inflammatory serum biomarkers correlate with VV density and are more elevated in unstable AAA.

APPROACH

The study protocol was approved by the Institutional Review Board (IRB) of the University of Pittsburgh. The study was funded by the AGS GEMSTAR award from the Society of Vascular Surgery (SVS) foundation in addition to the National Institute of Health (NIH) through a R03 grant.

Study Design

The objective of this study was to non-invasively study the metabolic processes within the aortic wall that are thought to explain aortic growth. This was a single center prospective evaluation of patients with an AAA diameter of at least 4.0 cm. enrolled between December

2011 and December 2016, in the outpatient vascular clinic. Patients were followed up until October 2019.

Aneurysm diameter size was determined on duplex ultrasound. Patients were excluded if they had contraindications to the administration of Definity contrast, such as pulmonary hypertension, unstable cardiopulmonary conditions, known right-to-left cardiac shunting and pregnancy. Patients underwent CEUS and serum PIB testing at enrollment and every 6 months up for 18 months or until eventual repair. PIB testing was also done one year after AAA repair..

CEUS imaging protocol

Patients were positioned on their back in the non-fasting state. An intravenous line was placed by the research staff at the time of the office visit. The abdominal aorta was imaged initially without contrast administration. Following non-contrast duplex imaging, CEUS was performed via intravenous administration of the ultrasound contrast agent, Definity® (Lantheus). 1ml of the contrast agent was diluted in 9ml of normal saline to achieve a concentration of approximately 10 microliters/kg. For each injection sequence, 0.5 mL contrast was injected over 2-3 sec during simultaneous burst replenishment real time imaging. Two injection sequences were typically performed. Each CEUS evaluation took approximately 20-30 minute to complete. Patient's heart rate, blood pressure and breathing were monitored during the examination and afterwards in the waiting area. The total monitoring time ranged between 30-90 minutes. Microbubble replenishment was analyzed using ImageJ (NIH) via manually drawn regions of the aortic wall and intraluminal thrombus (ILT) (Figure 1).

Ultrasound evaluation was performed using the GE US system (GE Healthcare, Chicago, IL, USA) with the standard curved array abdominal transducer. The contrast settings on the ultrasound system were set to a low mechanical index of 0.07 and a dynamic range of 50 with the focal zone placed underneath the posterior aortic wall.

Microbubble uptake was determined by the ultrasound technologist and the location was recorded on a study sheet. Uptake was then separately recorded by two of the investigators (RC, PC). Care was taken to correlate with color flow duplex ultrasound to avoid lumbar and mesenteric vessels as well as artifact. The visualization of the microbubbles within the

abdominal aortic aneurysm wall was defined as contrast uptake. This was determined by consensus agreement between the ultrasound sonographer and two investigators (The PI, RC and PC) for every single patient.

Uptake was quantified via video intensity analysis in a region of interest in the aortic adventitia. Background-subtracted peak video intensity, which has been shown to correlate with VV density, was derived and normalized to peak intensity in the lumen (Figure 2).⁹

Aneurysm growth, rupture and repair were recorded during the follow up period. Matched controls with no aneurysm disease underwent one-time CEUS and PIB testing using biomarker panels (Meso scale discovery) and Bioplex 100 analyzer (Bio-rad).

Biomarker testing

Blood samples were withdrawn from patients at each visit and one year following AAA repair. Blood was drawn in the Vascular Surgery clinic by the research staff. Blood samples were banked and used for the measurement of biomarkers. This is the list of plasma inflammatory biomarkers that were tested: Osteoprotegerin (OPGN), Galectin 3, Cystatin C, Neutrophil gelatinase-associated lipocalin (NGAL), Uromodulin (UMOD), C-reactive protein (CRP), Macrophage migration inhibitory factor (MIF), Intercellular adhesion molecule (ICAM1), Interferon γ (IFN- γ), Interleukin 10 (IL10), Interleukin 6 (IL6), Interleukin 8 (IL8), Tumor necrosis factor- α (TNF- α), Serum amyloid A (SAA), Vascular cell-adhesion molecule (VCAM1).

Statistical analysis plan: Sample size: No previous literature has reported the mean and standard deviation of AAA VV density measured in vivo by CEUS. Statistical analysis: Data will be summarized as mean and SD for continuous variables after testing for normality.

Categorical data will be summarized with frequency and percentage. Correlation coefficients will be determined for the correlation of VV and microbubble density measured by CEUS, as well as serum biomarkers with AAA growth. We will use linear regression to test the significance of such higher VV and microbubble density by CEUS as predictor of AAA growth (Aim1). We will include serum biomarkers in the modeling process. Adjustment for any

demographics differences will be also attempted including age, gender and race. A p-value <0.05 will determine significance.

Anticipated findings and alternative approaches: We anticipate that this clinical research study will identify biomarker and CEUS differences in AAA adventitial VV density based on age, gender and AAA stability or growth. Our findings will support a larger clinical trial and future investigations of treatment paradigms of AAA based on biologic risk of growth or rupture instead of absolute diameter. If CEUS and biomarker differences are not detected during the study period in otherwise stable AAA, longer follow up with repeated imaging and biomarker testing at 6month intervals will be sought. If our hypothesis is not confirmed (i.e. differences in AAA wall neovascularization do not exist), imaging of AAA wall inflammation will be considered when available to human subjects using microbubbles targeted to either activated leucocytes or endothelial cell adhesion molecules that are upregulated in inflammation and mediate leukocyte recruitment and adhesion. If CEUS is not accurate given the depth of penetration of ultrasound, alternative imaging modalities such as IVUS or FDG-PET CT scanning will be explored. We anticipate that our results will identify active angiogenesis and ischemia of the AAA wall and biomarker predictors of growth, which may improve real time monitoring of AAA progression and response to systemic or targeted microbubble anti-angiogenesis therapies.

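### The Aim 1 growth regression does not name baseline diameter as a covariate, and the plan does not say whether aneurysms above 5.4 cm belong in it

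*Combined protocol and SAP*

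**What the plan says.** The combined protocol and SAP gives two diameter ranges. Under Specific Aims, Aim#1 plans "prospective CEUS imaging of a cohort of patients with AAA 4-5.4cm in diameter at 6 month intervals for 18 months". Under Study Design, the enrolled population is "patients with an AAA diameter of at least 4.0 cm", with no upper limit.

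The exclusions in Study Design do not restore one: "Patients were excluded if they had contraindications to the administration of Definity contrast", and every example given there is a contraindication of that kind. Imaging runs "every 6 months up for 18 months or until eventual repair".

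The statistical analysis plan defines no analysis set and no diameter subgroup. Its Aim 1 test reads: "We will use linear regression to test the significance of such higher VV and microbubble density by CEUS as predictor of AAA growth (Aim1". On other model terms it says "We will include serum biomarkers in the modeling process", and that adjustment for any "demographics differences will be also attempted including age, gender and race". Baseline diameter is not named. The threshold is "A p-value <0.05 will determine significance".

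**The concern.** The scientific case rests on VV density carrying information that diameter does not. The background presents wall biology as an explanation for growth that absolute diameter leaves unexplained. The section on anticipated findings looks ahead to treatment based on biologic risk rather than diameter. A regression of growth on VV density that ignores diameter does not test that claim. Diameter may be a common cause: if larger aneurysms have denser VV and also grow faster, the two will correlate with no direct link between them.

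The two diameter ranges bear on the size of this bias. The wider the spread of an unadjusted common cause, the larger the association it induces. An open upper limit permits a wider spread than the 4-5.4 cm range of Aim#1. A reader of the plan cannot tell which of the two spreads applies.

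**Working it through.** **Text check.** Aim#1 has an upper limit and Study Design has none. Neither the exclusions nor the SAP settles which applies to the regression. Diameter is not a demographic variable, so it does not fall under the adjustment clause.

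**Figures in the plan.** The plan gives no sample size, effect size or SD, so it has no figure to reproduce. What follows is an illustration.

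**Taken from the documents.** Lower limit 4.0 cm, upper limit 5.4 cm (Aim#1), significance level 0.05.

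**Assumed.**
- 100 patients analysed and a two-sided test.
- Diameter D uniform on 4.0-5.4 cm, with a share p of patients uniform on 5.5-7.0 cm.
- VV density and growth each a straight line in D with independent residuals of constant variance, so no direct link.
- r is the correlation of D with each of the two within 4.0-5.4 cm.
- Large aneurysms carry full weight, and the other model terms remove none of the size effect.

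**Step 1, spread of diameter.** The two components have means 4.70 and 6.25 cm and variances 1.4²/12 = 0.1633 and 1.5²/12 = 0.1875.

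Var(D) = (1−p)·0.1633 + p·0.1875 + p(1−p)·(6.25−4.70)²

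k = Var(D)/0.1633

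**Step 2, correlation induced by size alone.**

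s = r²k / (r²k + 1 − r²)

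**Step 3, chance of p<0.05 (Fisher z).** With z = atanh(s)·√(100−3), the rate is Φ(z−1.96) + Φ(−z−1.96).

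**Worked case, p = 20% and r = 0.3.**
- Var(D) = 0.1307 + 0.0375 + 0.3844 = 0.5526, so k = 3.383.
- s = 0.3045/(0.3045 + 0.91) = 0.251.
- z = 0.2562 × 9.849 = 2.523, so the rate is Φ(0.563) = 71%.

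| Share at 5.5-7.0 cm | k | r = 0.1: s, rate | r = 0.2: s, rate | r = 0.3: s, rate |
|---|---|---|---|---|
| 0% (capped) | 1.000 | 0.010, 5% | 0.040, 7% | 0.090, 14% |
| 10% | 2.339 | 0.023, 6% | 0.089, 14% | 0.188, 47% |
| 20% | 3.383 | 0.033, 6% | 0.124, 23% | 0.251, 71% |
| 30% | 4.133 | 0.040, 7% | 0.147, 31% | 0.290, 84% |

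A simulation with 1,000,000 draws per setting agrees to within about one percentage point.

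**Dependence on sample size.** At r = 0.3 with 20% large, the rate is 42% for 50 patients and 95% for 200. Capped, it is 9% and 24%.

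**Step 4, with baseline diameter in the model.** The residuals of VV density and growth are independent given D, so the partial correlation is zero whatever p is. The simulation gave values within 0.002 of zero in every setting. Capping alone leaves s = r², which is 0.09 at r = 0.3.

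**The case against.** A reader might infer that every enrolled patient enters the growth regression, and hence that large aneurysms did enter it. The documents do not show this. The SAP labels the regression as Aim 1, and Aim#1 states its own range. Study Design may describe overall enrolment, which also serves the biomarker aim and the testing after repair. No count above 5.4 cm is given, and it could be zero. That objection stands: the mismatch is an ambiguity to resolve, and does not prove that larger aneurysms were analysed.

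A reader might also take the higher percentages as an estimate of the actual error. They are not. Every driver is assumed, and at r = 0.1 almost nothing happens. The straight line is extrapolated to 7.0 cm, so the nominal 0.3 case implies an overall correlation of diameter with VV density of √0.251 = 0.50 at 20% large and √0.290 = 0.54 at 30%.

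Full weight is also generous, because imaging stops at repair. Suppose half the large aneurysms give no growth value and the rest have doubled residual SD for growth (both assumed). At r = 0.3 with 20% large, the induced correlation is then about 0.17 instead of 0.25. The rate is about 41% instead of 71% with 100 analysed. The bias is smaller but remains.

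Finally, the open upper limit is not the root problem, since the adjustment removes the size-only association in this model with or without a cap. That is correct, and it is why the covariate comes first in the remedy. None of these objections supplies the missing covariate or says which range applies.

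**Conclusion.** Two findings rest on the text alone. The two diameter statements differ and the SAP does not say which governs the Aim 1 regression. Baseline diameter is not among the named adjustment variables. As written, the analysis cannot separate VV density from aneurysm size, and that separation is the study's central claim.

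How much this matters is conditional. It requires that VV density and growth both rise with diameter, which the documents do not establish. Under the assumptions set out above, the effect ranges from negligible at a within-range correlation of 0.1 to severe at 0.3 with many large aneurysms. Some confounding is possible even inside 4-5.4 cm, so settling the range would not be enough. The supportable statement is that size can create the association, not that it does.

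**What to change.** Add baseline duplex diameter as a prespecified covariate in the Aim 1 regression, and report the diameter-adjusted VV-growth association as the main result. In the straight-line model this removes the size-only association. If the relation with diameter is curved or diameter is measured with error, some of it will remain.

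Reconcile the diameter statements in Aim#1 and Study Design, and state in the SAP which range forms the Aim 1 analysis set. Report the number of patients above 5.4 cm. If any were enrolled, show the result both with and without them.

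The cost is one model covariate, one extra analysis and a few lines of SAP text. Diameter was already measured on duplex, so no new data are needed.

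### No masking is stated for the VV readings, so if follow-up readings enter the Aim 1 regression, which the plan leaves open, readers able to know growth to date could shift them towards the hypothesis

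*Combined protocol and SAP*

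**What the plan says.** All references are to the combined protocol and SAP.

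- **Aim#1** is to "Determine the relationship between AAA growth rate and VV density". Its hypothesis is directional: VV density is higher in aneurysms at risk for growth.
- **Study Design**, on the schedule: "Patients underwent CEUS and serum PIB testing at enrollment and every 6 months up for 18 months or until eventual repair". That allows up to four readings per patient. On size: "Aneurysm diameter size was determined on duplex ultrasound".
- **CEUS imaging protocol**, on the order within a session: "Following non-contrast duplex imaging, CEUS was performed via intravenous administration of the ultrasound contrast agent".
- **CEUS imaging protocol**, on the visual call: "Microbubble uptake was determined by the ultrasound technologist and the location was recorded on a study sheet". Next, "Uptake was then separately recorded by two of the investigators". The final call is joint: "This was determined by consensus agreement between the ultrasound sonographer and two investigators".
- **CEUS imaging protocol**, on the quantitative measure: "Microbubble replenishment was analyzed using ImageJ (NIH) via manually drawn regions of the aortic wall and intraluminal thrombus (ILT". Peak video intensity in a region of the adventitia is background-subtracted and normalised to the lumen.
- **Statistical analysis plan**: linear regression tests VV and microbubble density as a predictor of growth, with significance at p<0.05. It does not say which visit's reading is the predictor.

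The plan does not mention masking of any reader, reading in random order, a core laboratory or a check of reader agreement. It does not say who draws the regions.

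**The concern.** The predictor in Aim 1 depends on human judgement in two places: whether and where uptake is seen, and where the region is traced. Both judgements are made on patients who return every 6 months, in sessions that open with the imaging modality used to size the aneurysm. From month 6 on, the people reading VV therefore have the means to know how far the aneurysm has grown.

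A reader with that knowledge might look harder for uptake, or trace brighter wall, in an aneurysm that is growing. The error in the predictor would then depend on the outcome, and an association could appear with no biology behind it. It would run in the direction of the study hypothesis. The planned adjustment for age, gender, race and biomarkers would not remove it, because it is tied to growth itself. The results are meant to support a larger trial (Anticipated findings and alternative approaches), so a spurious association would carry forward.

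**Working it through.** **Step 1. Is the route open on the documents?**

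| Link | What the documents give | Status |
|---|---|---|
| Growth comes from diameter on duplex | Study Design | Diameter by duplex is stated |
| Duplex precedes CEUS in the session | CEUS imaging protocol | Stated |
| Diameter is measured in that session and seen by the readers | The two sections read together | Strong inference, not stated |
| The visual call includes the sonographer | CEUS imaging protocol | Stated, after separate recording by two investigators |
| The visual call guides the traced region | – | Not stated |
| Regions are drawn by hand | CEUS imaging protocol | Stated; analyst and masking not stated |
| Follow-up readings enter the regression | Statistical analysis plan | Left open |

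The likely Aim 1 predictor is the quantified intensity. The direct route to it is therefore the region drawing; the visual call matters only if it guides that drawing or is itself analysed.

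**Step 2. How large could the effect be?** The plan gives no sample size, power or effect size, so there is no figure to reproduce. What follows is an illustration.

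Assumptions (none from the documents, except the four visit times): true VV is independent of growth; VV and growth have SD 1; the within-patient VV correlation is 0.6; the test is two-sided at 0.05. The reading is shifted by b = 0.2 SD per SD of 18-month growth, in proportion to growth to date. The shift fractions at 0, 6, 12 and 18 months are thus 0, 1/3, 2/3 and 1.

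Induced correlation:

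- Enrollment reading: shift 0, so r = 0.
- Last reading: r = b/√(1 + b²) = 0.2/√1.04 = 0.196.
- Mean of four: the average shift fraction is (0 + 1/3 + 2/3 + 1)/4 = 0.5, so the shift is 0.1. The variance of the mean before the shift is 0.6 + 0.4/4 = 0.7. Then r = 0.1/√(0.7 + 0.01) = 0.119.

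Rejection probability by Fisher z, with z = atanh(r)·√(N−3) and P = Φ(z − 1.96) + Φ(−z − 1.96). For N = 50, √47 = 6.856:

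- Last: z = 0.1987 × 6.856 = 1.362; P = 0.275.
- Mean of four: z = 0.1192 × 6.856 = 0.817; P = 0.127 + 0.003 = 0.129.
- Enrollment: z = 0; P = 0.050.

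A simulation of the same model (8,000 runs per setting) agrees. False-positive rates at b = 0.2:

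| Predictor | N=30 | N=50 | N=100 |
|---|---|---|---|
| Last reading | 17.5% | 28.9% | 50.9% |
| Mean of four | 9.5% | 13.1% | 21.8% |
| Enrollment reading | 5.3% | 5.0% | 4.8% |

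**Step 3. Sensitivity to the assumed shift.** With the last reading and N = 50, the rate is 10.3% at b = 0.1, 53.5% at b = 0.3 and 91.6% at b = 0.5. With b = 0 (masked reading), or with the enrollment reading at any b, every simulated rate lies between 4.4% and 5.5%, which is the nominal 5% within simulation error.

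**The case against.** The case on the other side has several parts.

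- **Readers' knowledge is inferred.** A reader might infer that the diameter had just been measured when uptake was called, and that everyone in the consensus knew the growth. The documents do not say so. They give the sizing modality and the order of imaging, but not who measured diameter, when, or who had earlier values. This objection stands and limits the claim to a risk.
- **The visual call is not the likely predictor.** The quantified intensity is background-subtracted and normalised to the lumen. This stands in part. Those steps correct signal level, but they do not control where a person traces the region.
- **Two investigators recorded uptake separately before consensus.** This is a partial safeguard and deserves credit. It is not masking, and the consensus brings the sonographer's view back in.
- **An enrollment reading cannot follow later growth.** This stands, and it is the main condition on the point. Treating VV as a predictor makes an early reading a natural choice. Follow-up also ran to October 2019, about 34 months after enrollment closed in December 2016, so some growth may fall after every reading. Yet the plan collects serial readings and does not say which one is used.
- **The percentages depend on assumed inputs.** They do: nothing in the documents supports a particular shift or N.

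A reader might also infer that no change to the regression could help. That goes too far: using a reading taken before the growth it predicts removes this mechanism.

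**Conclusion.** The point holds as a conditional risk of bias. The documents state no masking for the visual call or for the hand-drawn regions, and they leave open whether follow-up VV readings enter Aim 1. If they do, and if readers know growth to date, the readings could move towards the hypothesis.

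The size cannot be fixed from the documents. Under the assumed model the excess over 5% ranges from small (mean of four readings, N = 30: 9.5%) to large (last reading, N = 100: 50.9%) at the same 0.2 SD shift. It is absent with the enrollment reading. Even that reading is made with current size visible and possibly with earlier surveillance growth known, so masking still has value there.

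The documents do not support the conclusion that the readings were biased or that an observed association would be spurious. This is a change the sponsor should make, with medium confidence.

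**What to change.** 1. **Masked reading.** Have the existing readers draw, or redraw, the ImageJ regions on stored CEUS clips with identity, visit date, callipers, earlier scans and biomarker results removed. Shuffle the clips across patients and visits. The plan does not mention stored clips; they are assumed to exist because ImageJ analysis needs recorded images. State who draws the regions.
2. **Technologist's role.** Limit the on-site call to flagging lumbar or mesenteric vessels and artefact, with no vote in the uptake result.
3. **Timing in the model.** State in the SAP that Aim 1 uses the enrollment reading, or the reading at the start of each interval, to predict subsequent growth.
4. **Agreement.** Report agreement between the readers on the masked readings.

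The cost is time for de-identification and re-reading; no new scan, visit or reader is needed. One limit remains: whoever traces the wall still sees the aneurysm's current size, so masking hides growth better than it hides diameter.

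### The growth regression names no baseline AAA diameter, so by itself it cannot separate a VV association from a size association

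*Combined protocol and SAP*

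**What the plan says.** Aim 1 is stated as "Determine the relationship between AAA growth rate and VV density". The statistical analysis plan proposes correlation coefficients and a linear regression of growth on VV and microbubble density. It then says "We will include serum biomarkers in the modeling process" and that adjustment for any "demographics differences will be also attempted including age, gender and race". No other covariate is named in the supplied text.

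Diameter is available: Study Design says "Aneurysm diameter size was determined on duplex ultrasound". Its schedule is "Patients underwent CEUS and serum PIB testing at enrollment and every 6 months up for 18 months or until eventual repair", which gives visits at months 0, 6, 12 and 18. The CEUS imaging protocol has a non-contrast duplex scan before each contrast study. It says that growth was recorded, but not how it is computed.

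The diameter range is given in two ways. Aim 1 describes "prospective CEUS imaging of a cohort of patients with AAA 4-5.4cm in diameter at 6 month intervals for 18 months", whereas Study Design describes "patients with an AAA diameter of at least 4.0 cm" with no upper limit.

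The background before the Specific Aims presents wall biology as accounting for growth that diameter leaves unexplained. The section on anticipated findings looks to later work on managing AAA by biologic risk in place of diameter.

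**The concern.** The rationale is a conditional statement: among aneurysms of the same size, those with more VV grow faster. The named model estimates a marginal association. If larger aneurysms have both more VV and faster growth, a VV coefficient can be significant although VV adds nothing to diameter. The word for an open list in the covariate sentence does not help, because that list is of demographics and diameter is not one.

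What is at stake is the interpretation of a positive result. A reader who has seen the rationale could take it as support for moving away from diameter, when the analysis has not addressed that question.

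**Working it through.** The plan gives no sample size, correlation or power, so there is no figure to reproduce. Every rate below rests on assumed values, with a two-sided 0.05 test (the plan does not state sidedness).

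**1. Without diameter in the model.** Suppose VV relates to growth only through diameter. Then r(VV, growth) = r(VV, diameter) × r(diameter, growth). With δ = atanh(r)·√(n−3), the rejection rate is Φ(δ−1.96) + Φ(−δ−1.96). Example, both correlations 0.3 and n=100: r = 0.09, δ = 0.0902 × 9.849 = 0.889, rate = 0.142 + 0.002 = 14.4%.

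| Both correlations | Induced r | n=50 | n=100 |
|---|---|---|---|
| 0.1 | 0.01 | 5.1% | 5.1% |
| 0.2 | 0.04 | 5.9% | 6.8% |
| 0.3 | 0.09 | 9.5% | 14.4% |
| 0.4 | 0.16 | 19.8% | 35.6% |
| 0.5 | 0.25 | 41.7% | 71.1% |

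These are error rates for the beyond-diameter reading only, not for Aim 1.

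**2. Narrow range.** Suppose the 4-5.4 cm range halves the diameter SD (k = 0.5). Each correlation r becomes kr/√(k²r² + 1 − r²). For r = 0.5: 0.25/√(0.0625 + 0.75) = 0.277, induced r = 0.077, rate 11.8% at n=100. For 0.3 and 0.4 the restricted correlations are 0.155 and 0.213, and the rates are 5.6% and 7.3%.

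**3. Diameter added, measured without error.** In simulation (n=100, 2,000 runs, correlations 0.3 and 0.5, diameter uniform on 4-7 cm or 4-5.4 cm) the adjusted VV term is rejected in 4.6% to 5.5% of runs.

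**4. Diameter added, measured with error.** If growth uses the month-0 reading, error in that reading enters growth with a negative sign and also enters the covariate. Simulation: n=100, 20,000 runs, readings at months 0, 6, 12 and 18 with independent equal errors, month-0 reliability 0.8 in the unrestricted range, true 18-month growth SD half the unrestricted diameter SD, and no VV effect beyond true diameter.

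| Range | Correlations (unrestricted) | Growth measure | Unadjusted | Adjusted |
|---|---|---|---|---|
| Unrestricted | 0.3 | four-visit slope | 8.6% | 12.4% |
| Unrestricted | 0.3 | slope, months 6-18 | 6.5% | 5.2% |
| Unrestricted | 0.5 | four-visit slope | 31.7% | 32.8% |
| Unrestricted | 0.5 | slope, months 6-18 | 17.7% | 5.6% |
| SD halved | 0.3 | four-visit slope | 4.9% | 7.8% |
| SD halved | 0.4 | four-visit slope | 5.9% | 11.8% |
| SD halved | 0.5 | four-visit slope | 7.1% | 17.9% |

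The narrow range is harder because reading error does not shrink with it. Error variance is 0.2/0.8 = 0.25 of the unrestricted true variance. Halving the SD leaves a true variance of 0.25, so reliability falls to 0.25/(0.25 + 0.25) = 0.5. The harm is not universal: with the SD halved, unrestricted reliability 0.9 and growth SD equal to the unrestricted diameter SD, adjustment is about neutral (5.5% to 5.7%, 6.9% to 6.8%, 10.9% to 9.7% at correlations 0.3, 0.4, 0.5). With the later-visit slope the adjusted rate was 5.0% to 6.9% over eight unrestricted settings and about 5% to 6% with the SD halved.

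**5. Precision.** Slope variance is the reading-error variance divided by the sum of squared time deviations. In years, four visits give 0.5625 + 0.0625 + 0.0625 + 0.5625 = 1.25, so 1/1.25 = 0.8. Months 6, 12 and 18 give 0.25 + 0 + 0.25 = 0.5, so 1/0.5 = 2.0. The ratio is 2.5.

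**6. Power lost to the covariate.** Assume r(VV, growth) = 0.3 and no direct diameter effect. With ρ = r(VV, diameter), partial r = (0.3 − 0.3ρ²)/√((1−ρ²)(1−0.09ρ²)). At ρ = 0.3: 0.273/√(0.91 × 0.9919) = 0.287. At ρ = 0.5: 0.225/√(0.75 × 0.9775) = 0.263. Power at n=100 falls from 86.2% to 82.6% and 75.1%; at n=50, from 56.4% to 51.8% and 44.6%.

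**The case against.** The strongest reply is that nothing planned is wrong. Aim 1 asks for a relationship and the model estimates it. The analysis section plans no claim of value over diameter, and the section on anticipated findings leaves that to a larger trial. VV is an intensity normalized to the lumen, so it need not rise mechanically with size. A 4-5.4 cm cohort controls size partly by design. Diameter also reflects past growth, so adjusting for it may remove part of a true VV effect. All of this stands, and it limits the weight of the point.

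It does not remove the point. Restriction shrinks diameter variation without eliminating it, and Study Design does not state the upper limit. The documents give no correlation that would show the size effect to be small.

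The reply is also right that the obvious remedy can mislead. Entering month-0 diameter beside a growth measure built on the same reading raises the error rate in most of the narrow-range settings tried. The remedy must therefore keep the covariate reading out of the outcome.

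**Conclusion.** The point holds, at minor to moderate weight. The named model cannot by itself separate a VV association from a size association, and the study's rationale needs that separation. How much this matters is unknown. It is negligible if diameter correlates 0.2 or less with both VV and growth, and reduced if the narrow range applies. It is large only if the correlations are 0.4 to 0.5 over a wide range of diameters. Sample size, correlations, reliability and SD ratios are all assumptions.

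A reader might infer that the Aim 1 analysis is invalid, or that the study can say nothing about its rationale. The documents support neither. Aim 1 is not stated as conditional on diameter, and the entry range in Aim 1 gives partial control of size. Nor do the figures show that a positive VV result would be false; they show what could happen under correlations that the documents do not report.

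**What to change.** - Keep the unadjusted analysis for Aim 1, and state how growth is computed.
- Add a supportive model with continuous baseline duplex diameter plus age, gender and race, in which growth does not use the reading entered as the covariate. One form is a slope over months 6, 12 and 18 with month-0 diameter as covariate. This assumes that diameter is recorded at each visit.
- On that same outcome, report the VV coefficient with and without diameter, and the gain in R-squared from VV over diameter and demographics.
- Make no beyond-diameter statement from the unadjusted result.
- Show any model that adjusts for month-0 diameter while growth also uses that reading only with a warning about shared reading error.
- Reconcile the diameter ranges in Aim 1 and Study Design.
- Follow-up ended in October 2019. If analyses have already been run, label the added model as post hoc.

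**Cost.** No new type of measurement is needed, but power falls. For a VV-growth correlation of 0.3, VV-diameter correlation 0.3 and n=100, moving from the unadjusted four-visit slope to the adjusted later-visit slope takes power from 43.0% to 22.9% (reliability 0.8, growth SD half the diameter SD), or from 79.1% to 65.9% (reliability 0.9, equal SDs). A null adjusted result is therefore weak evidence. Patients repaired before two later readings drop out, and their number should be reported. Adjustment may also remove part of a true VV effect, which is why both estimates should be shown.
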